2. Objectives (include all primary and secondary objectives)

Primary Aim 1. Examine whether individuals who are randomly assigned to SUVO 20mg (oral) will be less likely to test positive for (i) cocaine and (ii) non-prescribed opioids on urine drug screens (UDS) and will self-report lower opioid and cocaine craving, relative to those receiving placebo.

Date: 09/19/2024

Principal Investigator: [name].

Application Number: IRB00341328

Secondary Aim 1. Examine whether, relative to placebo, SUVO 20mg will improve self-reported sleep quality and total sleep time, as assessed via a sleep diary and an actigraph-like device, and will reduce self-reported insomnia symptoms and wake after sleep onset (WASO).

Secondary Aim 2. Given previous work suggesting that Suvorexant has a good safety profile among patients using opioids and patients using cocaine, a secondary aim will test no between-group differences in the rate of adverse events between individuals assigned to Suvorexant and placebo.

Secondary Aim 3. Examine whether SUVO 20mg will be associated with lower stress reactivity, lower self-reported stress and negative affect, and greater positive affect, relative to placebo.

3. Background (briefly describe pre-clinical and clinical data, current experience with procedures, drug or device, and any other relevant information to justify the research)

Opioid/stimulant co-use is a public health crisis that is increasing in prevalence (Goodwin et al., 2021) and directly contributing to increases in overdose deaths and disproportionately impacting minority individuals (Townsend et al., 2022). Individuals engaged in opioid/stimulant co-use face a greater risk of treatment discontinuation and continued substance use (Levin et al., 2015).

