Chronic opioid exposure can produce supersensitivity in dopamine neurons that could (theoretically) increase the reinforcing effects of cocaine in persons with OUD (Strickland et al., 2022). This testable theory may explain why new onset stimulant use develops in persons who are receiving opioid agonist treatment of OUD, a trend that has been observed for decades but for which no effective treatment has ever been identified. The following proof-of-concept study will examine whether antagonizing the orexin system with suvorexant (SUVO) will reduce cocaine co-use in persons receiving methadone or buprenorphine treatment. SUVO is an FDA-approved medication for treatment of insomnia, that has also shown substantial promise in reducing opioid craving and withdrawal symptoms.

This approach is supported by preclinical evidence that orexin antagonism blocks morphine sensitization of the ventral tegmental area (Mazaheri et al., 2022) and interacts meaningfully with the reward pathway and may have both direct effects on cocaine use and indirect effects by way of reducing opioid sensitization (Aston-Jones et al., 2010). This is also supported by our Phase II study that showed SUVO 20mg produced significant and clinically-meaningful reductions in opioid craving, insomnia, and withdrawal in persons withdrawing from opioids, a good safety profile, no evidence of abuse potential, and no SUVO discontinuation symptoms (Huhn et al., 2022). Further support suggested that SUVO improved restful sleep and reduced wake after sleep onset among patients using cocaine (Suchting et al., 2020). Additionally, SUVO has an excellent safety profile; previous studies examining SUVO in populations who use substances reported no serious adverse events (Huhn et al., in press; Suchting et al., 2020). SUVO also has also been shown to have low abuse liability (Herring et al., 2016; Huhn et al., 2022), and does not produce withdrawal symptoms after discontinuation (Herring et al., 2016).

4. Study Procedures

- a. Study design, including the sequence and timing of study procedures (distinguish research procedures from those that are part of routine care).

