- 3) Currently receiving methadone or buprenorphine treatment for OUD and considered to be stable on current dose for at least 30 days;
- 4) Willingness to engage with study protocol,
- 5) Use of birth control (as appropriate),

Exclusion criteria:

- 1) Psychiatric or medical conditions that are judged by the investigators to interfere with participation or that are contraindicated for use with SUVO,
- 2) Pregnant or breastfeeding,
- 3) Current use of benzodiazepines, tranquilizers, or other schedule IV sleep medications,
- 4) Moderate or severe substance use disorder other than opioid, stimulant, or cannabis use disorder;
- 5) SUVO consumption in the last 30 days,
- 6) Use of medications that are contraindicated with the study;
- 7) Past 30-day suicidal behavior,
- 8) Use of continuous positive airway pressure (CPAP) device for sleep apnea.

6. Drugs/ Substances/ Devices

a. The rationale for choosing the drug and dose or for choosing the device to be used.

Suvorexant (SUVO) is a dual orexin receptor antagonist (DORA) and an FDA-approved medication for treating insomnia. The 20mg dose is the maximum approved dose for use by the FDA. Our recent study demonstrated that a dose of SUVO 20mg reduced craving, insomnia symptoms, and withdrawal in persons undergoing opioid withdrawal (Huhn et al., 2022). Other research groups have found SUVO can improve restful sleep and reduced wake after sleep onset among individuals using cocaine (Suchting et al., 2020). SUVO has a strong safety profile, low abuse liability, and dose not produce withdrawal symptoms after discontinuation (Huhn et al., 2022; Suchting et al., 2022; Herring et al., 2016). Importantly, SUVO is hypothesized to restore

Date: 09/19/2024

Principal Investigator: [name].

Application Number: IRB00341328

dopaminergic functioning, which we believe is disrupted in persons who are co-using opioids and stimulants and is the mechanistic reason we are evaluating SUVO in this study.

- b. Justification and safety information if FDA approved drugs will be administered for non-FDA approved indications or if doses or routes of administration or participant populations are changed.

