We are proposing to administer SUVO 20mg, which is an FDA-approved dose. We are not requiring insomnia as an inclusion criterion in order to focus more specifically on opioid-stimulant co-use behaviors. We have collected substantial evidence that SUVO is safe and does not increase risk of misuse in persons with OUD (see Huhn et al., 2022).

- c. Justification and safety information if non-FDA approved drugs without an IND will be administered.

SUVO is an FDA-approved medication. We are not submitting for an IND because the intervention is not intended to be reported to the FDA as a well-controlled study or for a significant label change, it is not intended to support a significant change in the advertising for the product, and it does not involve a route or dose level or patient population for which there is increased risk associated with use of the drug.

7. Study Statistics

- a. Primary outcome variable

Urine drug-screen results. Participants will complete a urine drug screen at each clinic visit. The presence or absence of non-prescribed opioids and/or cocaine will be recoded at twice-weekly sessions. The primary outcomes will be 1) the presence of absence of opioids at each screen, 2) the presence or absence of cocaine at each screen, and 3) the presence or absence of a screen that is negative for all illicit substances.

Self-reported opioid and cocaine craving. Participant will complete visual analogue scale measures of opioid and cocaine craving during each weekly visit. The average score across each visual analogue scale will be a primary outcome.

Opioid and cocaine cue reactivity. Participants will also complete visual analogue scales in the presence of drug cues. Average scores on visual analogue scales will serve as a primary outcome

- b. Secondary outcome variables.

Insomnia Severity Index Scores. The Insomnia Severity Index is a seven-item screening measure of insomnia. Items are rated on a five-point scale. A cut score of 15 is typically used to demarcate clinical insomnia. The scale has been shown to have excellent psychometric properties, including among patients with substance use disorders.

Sleep Continuity. Using actigraphy and sleep-diaries (in which persons will be asked to report on their sleep the night before the assessment), we will focus on three commonly used sleep continuity outcomes: 1) total sleep time (TST), or the total number of minutes that an individual

Date: 09/19/2024

Principal Investigator: [name].

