Secondary Aim 1 and 3. To examine whether SUVO 20 mg improves 1) insomnia symptoms, 2) indices of sleep continuity, and 3) co-occurring affective symptoms relative to placebo, a series of mixed effects models will be conducted. For each model, we will include main effects of timepoint and medication group, as well as an interaction term. If the two treatment groups are systematically different on demographic or use characteristics at baseline, these measures will be included as covariates in the analysis. Models will involve a random intercept. Mixed effects models will also be used to compare drug cue reactivity at baseline and during the final week.

Secondary Aim 2. To compare SUVO 20mg to placebo on number of adverse events experienced, t-tests will be used.

Power analysis and sample size. A sample size of 40 will be used in this study. For all aims, we are sufficiently powered to detect moderate-to-strong effect, which has been observed in

Date: 09/19/2024

Principal Investigator: [name].

Application Number: IRB00341328

previous studies (e.g., Huhn et al., 2022). Due to our smaller sample size, effect size measures will also be considered.

All analyses will be conducted in SPSS and R. Two-tailed tests and an alpha level of .05 will be used.

d. Early stopping rules.

Participants will discontinue the study if the medical team determines it is not safe to continue in the study or if they request to discharge from the study. Additional stopping rules will include not abiding by study policies and procedures, or engaging in behaviors towards staff or other participants that are abusive. Finally, development of an intercurrent illness or condition that changes the participant's risk profile may result in a medically-related discharge from the study.

8. Risks

a. Medical risks, listing all procedures, their major and minor risks and expected frequency.

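### Section 7c's power statement is not supported for the sleep aim: its named example is a trial in people withdrawing from opioids, while this trial enrols dose-stable patients without requiring insomnia

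*Combined protocol and SAP*

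**What the plan says.** Section 7c sets the size and the claim: "A sample size of 40 will be used in this study", and then "For all aims, we are sufficiently powered to detect moderate-to-strong effect, which has been observed in" earlier work. One trial is named there, as an example. No effect size, standard deviation, within-person correlation, power percentage or dropout allowance is given. On testing: "Two-tailed tests and an alpha level of .05 will be used".

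Section 3 (Background) describes the named trial as showing "clinically-meaningful reductions in opioid craving, insomnia, and withdrawal in persons withdrawing from opioids". Section 6a describes it the same way.

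This trial's population differs. Inclusion criterion 3 (section 5) asks for methadone or buprenorphine patients "considered to be stable on current dose for at least 30 days". Section 6b states: "We are not requiring insomnia as an inclusion criterion in order to focus more specifically on opioid-stimulant co-use behaviors".

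Secondary Aim 1 (section 2) nevertheless looks for improvement in sleep quality, total sleep time, insomnia symptoms and wake after sleep onset. The models for it in 7c contain timepoint, group, their interaction and a random intercept. Covariates enter only if the arms differ at baseline on demographic or use characteristics. Section 7b says of the ISI: "A cut score of 15 is typically used to demarcate clinical insomnia". That cut-off is used for neither entry nor analysis.

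**The concern.** A power statement carries over to a new trial only if the effect it assumes is plausible in the new population. People in opioid withdrawal and people stable on an agonist for at least 30 days may differ in how disturbed their sleep is. Participants who already sleep adequately have less room to improve on the ISI or on wake after sleep onset. If a material share of the 40 are in that position, the average treatment difference shrinks. Section 7c makes no allowance for this and does not say what share is expected.

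At stake is the reading of a null result. If the all-participant comparison of ISI or wake after sleep onset shows no difference, the natural summary would be that suvorexant does not help sleep in co-users. The same result could arise because many participants slept acceptably at entry, or because the comparison was too small. As written, the plan has no prespecified estimate that would help to tell these apart.

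**Working it through.** **Inputs.** From section 7c: N = 40, two-sided alpha .05. Assumed, because not stated: 1:1 allocation (20 per arm), no dropout, common SD unchanged by mixing participants with and without insomnia. Also not in the documents: the cited effect size, the fraction *f* with insomnia, and the within-person correlation. Benchmarks d = 0.5 and d = 0.8 stand in for the moderate and strong ends of the claim; *f* is shown as a range.

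**Step 1: the plan's own figure.** There is none to reproduce. The claim is qualitative.

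**Step 2: power before any dilution.** Two-sample t-test, 38 degrees of freedom, noncentrality d × √(20/2), critical value 2.024.
- d = 0.5: noncentrality 1.58, power 34%.
- d = 0.8: noncentrality 2.53, power 69%.
- 80% power is reached only at d = 0.91.

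**Step 3: dilution, single comparison.** Let d = 0.8 hold in those with insomnia and let the rest gain a share *k* of it. Average effect = 0.8 × [f + k(1 − f)].

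| f | k = 0: average d | power | k = 0.5: average d | power |
|---|---|---|---|---|
| 100% | 0.80 | 69% | 0.80 | 69% |
| 80% | 0.64 | 51% | 0.72 | 60% |
| 60% | 0.48 | 32% | 0.64 | 51% |
| 40% | 0.32 | 17% | 0.56 | 41% |

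**Step 4: allowing for repeated measures.** For the mean of eight visits with correlation 0.5, the variance factor is (1 + 7 × 0.5)/8 = 0.5625. Adjusting for one baseline value subtracts 0.5² = 0.25, leaving 0.3125. Effective d = average d / √factor. No gain is assumed in those without insomnia.

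| f | d = 0.8, eight visits | d = 0.8, eight visits, baseline-adjusted | d = 0.5, eight visits, baseline-adjusted |
|---|---|---|---|
| 100% | 91% | 99% | 79% |
| 80% | 75% | 94% | 60% |
| 60% | 51% | 75% | 38% |
| 40% | 26% | 42% | 20% |

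Dilution lowers power in every row. How far, and from what starting point, depends on inputs that the plan does not give. The eight-visit columns also assume that the sleep outcome is recorded at all eight visits; section 4a gives no ISI schedule.

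**The case against.** The strongest reply is that the loss cannot be sized from the documents, and that is right. Section 7c states no power for the sleep aim to fall below, so a reader who infers that power drops well short of a stated figure goes further than the text allows. The dilution model also assumes that the benchmark effect belongs to people with insomnia. The named trial is described only as enrolling people in withdrawal, with no insomnia entry rule. If its sample was mixed, its effect is already partly diluted. It is cited only as an example, and sections 3 and 6a also report better sleep with suvorexant in people using cocaine, a group closer to this one. No effect size is given for that study, and 7c does not name it.

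Zero effect below ISI 15 is an extreme assumption too. The cut-off marks clinical insomnia, not the point at which sleep stops being improvable. A reader might infer that restricting to ISI ≥ 15 recovers power. Under d = 0.8 with no gain in the rest it does: 59/47/32% in the subset against 51/32/17% overall, at 80/60/40%. If the rest gain half, the all-participant test is ahead at 60/51/41%. So the subset cannot be justified on power.

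The planned models use repeated measures, and with baseline adjustment power can be high. That adjustment is not specified, however, and 7c does not say whether baseline is one of the timepoints.

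A reader might also infer that a null sleep result would undermine a sleep-based explanation of reduced drug use. No mediation analysis is planned, and the mechanism given in 6a is dopaminergic.

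Finally, this is a pilot, sleep is secondary, omitting insomnia is a reasoned choice for the primary aim, and 7c says effect sizes will be considered. These points lower the weight of the concern. They do not supply a basis for the power statement.

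**Conclusion.** The concern holds in a limited form. The power statement in 7c covers the sleep aim without a stated effect, without allowance for a dose-stable population in which insomnia is not required, and without a role for baseline sleep severity in the analysis. It is therefore not supported for Secondary Aim 1.

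The firmest numbers are those that need no dilution: 34% power at d = 0.5 and 69% at d = 0.8 for a single comparison with 20 per arm. The further loss is conditional. At d = 0.8 and an 80% insomnia fraction it ranges from about 5 points (99% to 94%, eight visits, baseline-adjusted) to about 19 points (69% to 51%, single comparison; 18.8 before rounding), with no gain in the rest. At 40% it is larger in both settings. The direction rests on one premise, that people who sleep adequately gain less, which is plausible but is not shown in the documents.

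**What to change.** Leave eligibility unchanged.

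1. **Section 7c, power.** Stop applying the general power statement to Secondary Aim 1. Either label that aim as estimation, or state its power with the assumed effect, the correlation and a range of insomnia fractions. Note that the named example comes from people in opioid withdrawal, and that the study in cocaine users is cited without an effect size.
2. **Sections 4a and 7c, baseline sleep.** State that the ISI is completed at the baseline visit before the first dose. Adjust each sleep model for the baseline value of its outcome. Report with 95% confidence intervals, as estimation only, how the treatment difference varies with baseline ISI: either the treatment-by-baseline-ISI interaction, or the ISI ≥ 15 estimate beside the all-participant one. Add a sentence that a null overall result will not be read as absence of effect on disturbed sleep.

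The cost is protocol wording and one prespecified estimate per sleep outcome. The ISI is already among the listed measures and self-report measures are already completed at the randomisation visit, so no participants or procedures are added. The downside is a less favourable power statement and wide intervals for the baseline-ISI estimates.

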Screening visit(s). Screening procedures may be scheduled across more than 1 day to meet participant schedules. Prior to completing any study-related screening, participants will review and sign an informed consent form with a trained staff member. Participants will be given the opportunity to do an in-person or a remote consent. For participants that complete the remote consent, some screening procedures will also be completed remotely, including interviews and questionnaires. Participants who complete this initial eligibility screening will complete the remainder of their screening visit in person. During the screening visit, participants will be assessed for inclusion and exclusion criteria. A urine drug-screen will be collected to assess for recent drug exposure and pregnancy (when indicated), the Mini-International Neuropsychiatric Interview (M.I.N.I.), the Addiction Severity Index (McLellan, Cacciola, & Zanis, 1997), the Columbia Suicide Severity Rating Scale, a demographic questionnaire, and a health form assessing current conditions and medications will be used to help evaluate participant eligibility.

Baseline/Randomization visit. Following determination of eligibility, participants will be randomized (stratified by gender) to receive 20mg of SUVO (the maximum FDA approved dose) or placebo. Randomization will occur prior to visit 1. At the randomization visit, participants will provide a urine sample that will be tested for recent drug use and complete self-report measures as described below. They may also complete a cue-induced craving paradigm, a probabilistic reward task, and the Trier Social Stress Test (TSST) described below. Participants will also be provided with an actigraph-like device to wear for the duration of their study participation to assess sleep.

Medication dispensing will begin during the baseline session. Participants will receive a blister package with 7-days of medication dispensed as two capsules (10mg SUVO or placebo) so that medication doses can be reduced to 50% of the dose if requested by a

Date: 09/19/2024

Principal Investigator: [name].

Application Number: IRB00341328

participant. Participants will also receive a 3-day blister package as a contingency strategy in case of missed visits. Participants will be instructed to return blister packages once weekly as a measure of medication compliance.

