- Medication Satisfaction and Blinding: Medication satisfaction and a question assessing whether participants believe they received the active or inactive medication will be collected at the final study visit.
- Caffeine intake: A self-report measure of caffeine use will be given.
- Fagerstrom Test for Nicotine Dependence: This is a validated measure of problematic nicotine use.
- Distress intolerance. The Distress Intolerance scale will be used to identify the extent to which individuals have difficulty tolerating aversive states.

- Affect-based impulsivity. The UPPSP impulsive behavior scale is a measure of five subtypes of affect impulsivity: positive urgency, negative urgency, lack of perseverance, lack of premeditation, and sensation seeking.
- Visual Analog Ratings: Participants will be asked to complete visual analogue scales assessing craving substances, at each assessment and, at some timepoints, when presented with visual cues.
- Trier Social Stress Test: Trier Social Stress Test (TSST; Kirschbaum et al., 1993), a 15-minute, well-validated psychosocial stress induction paradigm in which participants are asked to prepare and perform a speech, as well as mental arithmetic, in front of an experimenter.
- Probabilistic Reward: Participants will be asked to complete a validated probabilistic reward task (Pizzagalli et al., 2008), in which they will be asked to discriminate between two similar stimuli, one is associated with a higher degree of reward. This task takes approximately 25 minutes and is a behavioral measure of anhedonia.
- Brief Pain Inventory: Participants will self-report their pain symptoms, and pain interference.
- Insomnia Severity Index: Participants will self-report insomnia symptoms.
- Positive and Negative Affect Schedule: The PANAS will be used to assess changes in affect as a function of study medication. It will be administered at screening, during weekly visits, and end of study.
- Pittsburgh Sleep Quality Index: The PSQI is a validated measure of sleep quality and sleep patterns.
- Perceived Stress Scale: Participants will self-report their perceived stress.
- GAD-7: The GAD-7 is a 7-item self-report measure of anxiety symptoms.
- Sleep Diary: Participants will self-report their previous nights sleep.
- Subjective Opiate Withdrawal Scale: Participants will self-report whether they are experiencing opioid withdrawal symptoms.

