Application Number: IRB00341328

is asleep, 2) wake after sleep onset (WASO), or the total number of minutes that an individual is awake after sleep onset and prior to awakening, and 3) subjective sleep quality.

Co-occurring affective symptoms. Participants will be assessed for positive and negative affect using the PANAS. Participants will report perceived stress using the Perceived Stress Scale (PSS) is a 10-item measure of perceived stress. Items are rated on a five-point scale.

Abuse Liability Assessments (i.e., Medication Satisfaction Questionnaire). Participants will be asked to complete abuse liability measures. Participants will also be assessed for adverse events and serious adverse events in each visits. The abuse liability of the blinded study drug will be assessed by asking participants to rate “drug effects”, “good effects”, and “bad effects”, on a 0-100 point VAS, with 0 being “None” and 100 being “Extremely”. Participants will also report the perceived street value of the study drug. These subjective drug effect ratings are considered by the FDA to be the gold standard for assessing abuse liability.

Adverse events We will follow standard FDA guidelines regarding adverse events. Participants will be able to self-report adverse events via a study contact number. Events will be documented on a standardized form that adheres to FDA standards for adverse event reporting (e.g., event, system affected, start and stop date/time, perceived relationship to the study, severity, expectedness).

c. Statistical plan including sample size justification and interim data analysis.

Primary Aim 1. To examine whether SUVO 20mg reduces opioid and cocaine use and craving relative to placebo, a series of mixed models will be conducted. For analyses with a binary outcome (i.e., use at each assessment), generalized logistic models will be used, and for analyses with a continuous outcome (i.e., craving), linear mixed models will be used. Mixed effects models will also be used to compare drug cue reactivity at baseline and during the final week. For each model, we will include main effects of timepoint and medication group, as well as an interaction term. If the two treatment groups are systematically different on demographic or use characteristics at baseline, these measures will be included as covariates in the analysis. Models will involve a random intercept.

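### Section 7c lets chance baseline imbalance choose the covariates, instead of always adjusting for gender (the randomisation stratum) and the outcome's own baseline value

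*Combined protocol and SAP*

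**What the plan says.** The covariate rule is in section 7c under Primary Aim 1 and is repeated for Secondary Aims 1 and 3: "If the two treatment groups are systematically different on demographic or use characteristics at baseline, these measures will be included as covariates". Neither place gives a test, a threshold or a list of variables. The fixed part of every model is: "For each model, we will include main effects of timepoint and medication group, as well as an interaction term", with a random intercept. Gender and the baseline value of the outcome are not among the fixed terms.

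Section 4a (Baseline/Randomization visit) makes gender the stratum: "participants will be randomized (stratified by gender) to receive 20mg of SUVO". The same paragraph provides baseline data: "At the randomization visit, participants will provide a urine sample that will be tested for recent drug use and complete self-report measures". In the list of measures in 4a, participants are to "complete visual analogue scales assessing craving substances, at each assessment", so baseline craving is available. Baseline cue reactivity is less certain: "They may also complete a cue-induced craving paradigm".

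Cue reactivity alone has a stated time comparison: "Mixed effects models will also be used to compare drug cue reactivity at baseline and during the final week".

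**The concern.** Under randomisation, a baseline difference between arms is chance. A rule triggered by such differences therefore picks variables by accident, whatever their relation to the outcome. Three consequences follow.

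- **Gender.** It could enter as a demographic, but stratification tends to balance it, so the rule is unlikely to select the one variable the design singles out.
- **Baseline value.** Baseline urine can count as a use characteristic. A craving score is arguably neither demographic nor use, so for craving the rule may not apply at all.
- **Cue reactivity.** Comparing baseline with the final week through a group-by-time term makes baseline an outcome row. The interaction is then a change-from-baseline test, which is less precise than adjusting for baseline.

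In a 40-person pilot that plans two-tailed tests at .05 and will also read effect sizes, this is precision given up on data already planned. In the logistic models the odds ratio also depends on which covariates are included, so a covariate set chosen from the data changes what is being estimated.

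**Working it through.** **Inputs from the documents.** N = 40; two-sided alpha .05; random intercept; one baseline visit and 8 twice-weekly visits (section 4c). The plan gives no numerical effect size, SD or power target, so it has no power figure to reproduce.

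**Assumptions.** 1:1 allocation (20 per arm); single-visit SD of 1; constant within-person correlation r of 0.3, 0.5 or 0.7; constant effect of 0.5 SD; no missing visits. The rows for the rule assume that it can reach the baseline value.

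**Step 1: variances, with no effect size needed.** For the mean of k post-baseline visits, the per-person variances within an arm are:
- unadjusted: V = (1 + (k−1)r)/k
- change from baseline: V + 1 − 2r
- adjusted for baseline: V − r²

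Adjustment gains r² over unadjusted. It gains (V + 1 − 2r) − (V − r²) = (1−r)² over change. Neither gain can be negative.

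With k = 8:

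| r | Unadjusted | Change | Adjusted |
|---|---|---|---|
| 0.3 | 0.3875 | 0.7875 | 0.2975 |
| 0.5 | 0.5625 | 0.5625 | 0.3125 |
| 0.7 | 0.7375 | 0.3375 | 0.2475 |

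At r = 0.5 the standard error of the difference is √(2 × 0.5625/20) = 0.237 unadjusted and √(2 × 0.3125/20) = 0.177 adjusted.

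**Step 2: simulated power.** Tests are t-tests, or analysis of covariance where adjusted. The rule adjusts only when the baseline difference meets the trigger.

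| Analysis | r = 0.3 | r = 0.5 | r = 0.7 |
|---|---|---|---|
| Unadjusted | 69% | 54% | 43% |
| Rule, trigger p < .05 | 70% | 55% | 45% |
| Rule, trigger standardised difference > 0.2 | 75% | 67% | 63% |
| Change from baseline | 41% | 54% | 76% |
| Always adjusted | 79% | 78% | 86% |

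**Step 3: cue reactivity** (one baseline and one final-week value). The change test has roughly 25, 34 and 51% power; the adjusted test has about 36, 42–43 and 57%.

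**Step 4: decaying correlation.** If correlation falls by a factor of 0.8 per visit, power is about 51% unadjusted, 42% for change and 64% adjusted.

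**Step 5: gender** (r = 0.5). If gender is assumed to explain 10% of single-visit variance, including it raises power from 54% to 62% without baseline in the model, and from 78–79% to 81–82% with baseline. If it explains nothing, including it costs essentially nothing (77.3% v 77.2%).

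**Step 6: false positives.** With a fixed mechanical trigger the rule rejects a true null in about 2–5% of trials, so it is conservative.

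**Step 7: urine, approximate only.** These figures use each person's proportion of positive screens, not the planned logistic mixed model. At an assumed 70% v 50% positive, with random-intercept SD 1, 2 or 3, power is 69/47/39% unadjusted and 72/60/58% adjusted. At 90% v 75% (SD 2) it is 48% and 55%.

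**The case against.** The strongest reply is that the loss depends on how the trigger is read. Nothing in 7c says that a systematic difference means a significance test. With a standardised-difference trigger of 0.2, the rule fires in 53% of trials and recovers about half of the available gain; with 0.1 it reaches 77/72/74%. This stands. A reader might infer from the p < .05 row that the rule recovers almost nothing, but the documents do not fix that trigger. What survives is that every trigger tried falls short of always adjusting.

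It also stands that the gains are smaller when correlation decays, that gender adds only about 3 points at 10% of variance once baseline is in the model, and that urine may gain little if nearly everyone is positive at baseline, which is plausible for cocaine in people recruited because they use it.

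A reader might infer that the rule inflates the Type I error. With a mechanical trigger it does not. The opposite flat statement, that it cannot, is not supported either, because no trigger or variable list is stated. In a deliberately worst-case null simulation, the smallest p-value was reported over any subset of imbalanced covariates (standardised difference above 0.2). The pool was baseline plus four assumed covariates correlated 0.3 with the person effect. Rejection was about 12%, against about 5% unadjusted. Nothing in the plan says that anyone would do this; it simply leaves the room.

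**Conclusion.** The point holds as a low-cost improvement to a stated rule. It does not show that the trial is invalid. The direction rests on the random-intercept structure in 7c and needs no effect size: in large samples, baseline adjustment is never less precise than the unadjusted average or change from baseline. The size rests on assumed r, effect, allocation and trigger. At r = 0.5 it is 78% power against 55–67% under the two tabulated triggers and 54% for change; with decaying correlation it is 64% against 51% and 42%. Error above .05 is a possibility opened by the missing definition, not a demonstrated property of the plan.

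A reader might also treat the unnamed treatment term for urine and craving as part of this fault. Section 7a's statement, "The average score across each visual analogue scale will be a primary outcome", leans towards an average for craving but could mean over visits or over items, and it says nothing for urine. That is missing detail and a choice for the team, so it is only a side note here.

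**What to change.** In 7c, under both Primary Aim 1 and Secondary Aims 1 and 3, replace the imbalance sentence with:

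*All models include gender (the randomisation stratum) and, where collected, the baseline-visit value of the same outcome as covariates; baseline is not also an outcome row. A missing baseline value is set to the pooled mean. No covariate is added to the main analysis because of observed imbalance; any such model is a sensitivity analysis.*

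For urine, use the baseline result for the same substance or the same outcome definition. For cue reactivity, test the final-week difference between arms adjusted for gender and, where collected, the baseline value.

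The cost is a wording change and two degrees of freedom, with no new data or visits. If baseline is nearly unrelated to the outcome, under about 1 point of power is lost (at r = 0.1 with one post-baseline value, 33.9% unadjusted v 33.3% adjusted).

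Side note: name the treatment term for urine and for craving before unblinding. Which term is the team's choice.
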